primary outcome	measure (instrument, scale, source)	Single substance use question assessing the 28 days prior to baseline.		
Baseline for secondary outcome	variable	Volume of self-reported offending in the 6 months prior to baseline. Behaviour: internalising behavior and externalising behaviour at baseline. Mental health and wellbeing at baseline. Family cohesion and conflict at baseline. Alcohol and substance use problems at baseline. Self-report Client Service Receipt Inventory (CSRI) in the 6 months prior to baseline to assess police involvement (arrests, cautions, charges, court attendance), educational outcomes (suspensions, exclusions, managed moves) and employment status.		
	measure (instrument, scale, source)	Offending: Self-report delinquency questionnaire covering the previous 6-month (SRDS).		

Behaviour: Strengths and difficulties questionnaire (SDQ). internalising behaviour and externalising behaviour.

Mental health and wellbeing, Warwick-Edinburgh Wellbeing Scale-short form (WEMWBS-SF).

Family: Brief Family Relationship Scale (BFRS).

Alcohol and substance use problems, European School Project on Alcohol and Drugs Problem Scale (ESPAD-PS).

Self-report Client Service Receipt Inventory (CSRI).

Randomisation

The randomisation of young people to MDFT or BAU will be conducted by research staff after informed consent has been taken and the baseline assessment completed, by intake staff at Barnardo's. The allocation will involve an equal probability of receiving one of the two trial arms, MDFT or BAU, and will employ random permuted blocks of variable size (2, 4 or 6) with a random block seeded throughout. Randomisation will be conducted using a secure, independent randomisation service, Sealed Envelope Ltd. Randomisation will be stratified by geographical site (Bristol, Newport) and severity of substance use (low/ medium, high) ascertained using the GAIN-SS assessed at baseline. A full quality assurance AUDIT trail will be kept of all allocations and research staff will not be able to see future allocations. The allocated group will be relayed back to staff in the sites.

It is not possible, or appropriate, to blind young people or staff to their allocated group although follow-up at months 6 will be conducted by researcher's blind to participant allocation.

Participants

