Targeting those at the greatest risk of serious youth violence will be a key priority. The prioritisation of referrals will be decided using a multi-agency approach via intelligence sharing between Barnardo's, Local Authority and education safeguarding teams and Police across Bristol and Newport. It is expected that 70% of referrals will be secondary, not currently involved with CJS and 30% tertiary, currently involved with CJS. Referrals will come from services in Bristol and Newport who are in contact with vulnerable children with known or suspected substance use problems, including schools, Pupil Referral Units, Youth Offending Services, Children's Social Services, CAMHS and specialist drug and alcohol services. It is anticipated that most referrals will come through an agreed referral pathway with both Local Authorities (LA), of their Front Door arrangements, Youth Justice Teams and Violence Reduction / MACE arrangements. Following discussions with both LAs, Barnardo's is

confident that sufficient referrals will come from this pathway to meet the required numbers. In addition, referrals may also be made by other services. This is a similar approach to that adopted by Barnardo's Strategic Child Exploitation Service in Bristol which works directly with young people at the highest risk of harm - gang involvement, serious violence, and exploitation. Initial estimates suggest 35% of participants will be from Black, Asian or other racially minoritised groups, 35% will have special educational needs or disabilities, 15% will be care experienced and 35% female.

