Staff at Barnardo's will screen referrals to ensure they are consistent with the study inclusion and exclusion criteria and take informed consent. The principle of Gillick consent will be employed by staff trained in assessing Gillick competence to assess whether participants are mature and intelligent enough to make their own informed decisions. As a rule, young people aged 13 years or more, of average intelligence, are considered Gillick competent. Unless there is a specific reason not to do so, parents/ carers will be informed of the young person's participation in the study. Where consent cannot be taken using the Gillick principle, consent will be sought from a person with parental responsibility, in this scenario if a parent/ carer provides consent the young person will also have to provide assent to ensure there is no parental coercion to participate. Parent/carer consent is not required at the start of delivery. MDFT therapists will work with the young person to build their trust in the process and comfort with seeking parental/carer consent. They will also work to identify a trusted adult that could take the place of a parent/carer where needed. Broadly speaking, we would expect parents to be approached within a month of the young person starting MDFT. Giving young people the time and space to decide whether to approach a trusted adult, who it may be, and how they may approach them is crucial to the rapport building process.

It is anticipated that 60% of the referrals will come from Bristol and 40% from Newport, based on the relative population sizes. This means that 4 therapists will be recruited in Bristol and 3 in Newport. Based on our delivery in Bristol to young people being harmed in their communities through substance use, serious violence, and exploitation, we receive referrals showing a disproportionate percentage of racially minoritised young people. Following discussion with our referring partners in both LAs, we believe this pattern will be reflected in the MDFT pilot.

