On completion of assessment battery research staff receive automated message of a referral, randomisation conduct, allocation relayed back to Barnardo's staff who either initiate MDFT or make referral to BAU.

Randomised to BAU (200) Randomised to MDFT (200)

YP referred to alternative service YP allocated MDFT therapist

Outcome assessment at month 6 Outcome assessment at month 6 (n=182) (n=182)

Outcome assessment at month 12 Outcome assessment at month 12 (n=160) (n=160)

Data is collected at 6- and 12-months using bespoke, secure, on-line data collection system and transferred to secure servers managed by the University of Kent. Six- and 12-month data collection is completed by research staff blind to participant allocation and participants receive a payment of £25 for completing assessments at baseline 6- & 12 months.

Sample size calculations

Sample size estimation was conducted in STATA18. A clinically important effect size for substance use frequency in adolescents is estimated as 0.27, similar to the lower bound

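### Small permuted blocks, with their sizes printed, in an open trial make allocations partly predictable to the organisation that enrols; larger undisclosed blocks from the efficacy stage are a cheap improvement

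*Protocol*

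**What the plan says.** All references are to the protocol.

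- **Randomisation.** Allocation is 1:1, within strata formed by site (Bristol, Newport) and GAIN-SS severity (low/medium, high), and "will employ random permuted blocks of variable size (2, 4 or 6) with a random block seeded throughout". The list is held by an independent service. Research staff randomise after consent and baseline and cannot see future allocations. Young people and staff are not blinded. "The allocated group will be relayed back to staff in the sites".
- **Participants.** "Staff at Barnardo's will screen referrals to ensure they are consistent with the study inclusion and exclusion criteria and take informed consent". The same organisation judges Gillick competence and runs the baseline assessment. The section also says: "Targeting those at the greatest risk of serious youth violence will be a key priority".
- **Figure 3.** Completing the baseline battery triggers randomisation, with "allocation relayed back to Barnardo's staff who either initiate MDFT or make referral to BAU".
- **Business as usual.** BAU is provided by other services, and controls are offered nothing therapeutically similar to MDFT.
- **Appendix II.** The pilot progression criteria rate allocation balance overall (under 2% green, over 5% red) and by stratum (under 5% green, over 10% red).

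**The concern.** A concealed list does not stop inference from allocations already known. Small balanced blocks within four strata pull the running count back towards equality, so the arm that is behind is the better guess. The assurance about future allocations names research staff, not the people who enrol.

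The organisation that books and completes baselines also learns every past allocation. It delivers one arm only and has a stated priority to reach those at greatest risk. Someone who expected BAU next could postpone a high-need young person's baseline, or bring one forward when expecting MDFT. The arms would then differ in prognosis in ways that adjustment for the strata and one baseline frequency question removes only in part. The primary comparison at 6 months would carry that difference.

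**Working it through.** The protocol gives no predictability figure to reproduce, so this is a derivation.

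**Inputs.** From the protocol: sizes 2, 4 and 6; 1:1 allocation; four strata; 400 randomised; 60% Bristol and 40% Newport (240 and 160). Assumptions: sizes equally likely; severity split 50/50, giving strata of 120, 120, 80 and 80; random blocks, where modelled, are simple random (unbalanced).

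**Step 1: ceiling, exact.** The guesser picks the arm that is behind in the stratum and tosses a coin when the arms are level. Expected correct guesses in a block of 2m are m + (4^m / C(2m,m) − 1)/2.

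- Block of 2: 1 + (4/2 − 1)/2 = 1.5, or 75.0%
- Block of 4: 2 + (16/6 − 1)/2 = 2.833, or 70.8%
- Block of 6: 3 + (64/20 − 1)/2 = 4.1, or 68.3%
- Equal mix: (1.5 + 2.833 + 4.1)/12 = 8.433/12 = 70.3%

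This guesser needs neither the block sizes nor the block boundaries. The same formula gives 69.3% for 4/6, 68.1% for 4/6/8 and 66.5% for 6/8/10.

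**Step 2: next severity stratum unknown.** Severity comes from the GAIN-SS at baseline, after the screening and consent decisions. A guesser who follows only the site total scores about 64%. A Bayesian guesser who knows past allocations by stratum, but not the next person's severity, scores about 65%. With 10% or 25% simple-random blocks as well, the figure is about 62% or 60%.

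**Step 3: possible bias.** Suppose staff act only when at least 75% sure, and acting shifts expected outcome by 0.2 SD in the guessed direction. Bias is then the multiplier times 0.2, where the multiplier is the mean guessed direction in MDFT minus that in BAU.

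| Scenario (no random blocks unless stated) | Blocks | Predictable at ≥75% | Multiplier | Bias |
|---|---|---|---|---|
| Severity known | 2/4/6 | 59% | 0.805 | 0.16 SD |
| Severity known | 6/8/10 | 26% | 0.341 | 0.07 SD |
| Severity known, 10% random | 2/4/6 | 54% | 0.629 | 0.13 SD |
| Severity known, 10% random | 6/8/10 | 16% | 0.174 | 0.03 SD |
| Severity unknown | 2/4/6 | 20% | 0.27 | 0.05 SD |
| Severity unknown | 6/8/10 | 10% | 0.12 | 0.02 SD |
| Severity unknown, 10% random | 2/4/6 | 16% | 0.19 | 0.04 SD |
| Severity unknown, 25% random | 2/4/6 | under 1% | under 0.01 | near 0 |

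At a 0.1 SD shift every bias figure halves. Against the 0.27 target, 0.16/0.27 is about 60% and 0.05/0.27 is about 20%.

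**Step 4: what larger blocks cost in balance.** The largest imbalance from one unfinished permuted block is half the largest size: 6/2 = 3 now and 10/2 = 5 with 6/8/10. Relative efficiency is 1 − (d/n)². For d = 5 in a stratum of 80 it is 1 − (5/80)² = 0.996. If an unfinished pilot block added its own 3, the worst case is 1 − (8/80)² = 0.99.

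In the 60-person pilot the picture differs. Simulating without random blocks, and taking the difference as |MDFT − BAU|/n, the chance of a red overall rating rises from about 10% to 22%. The chance that at least one stratum is red rises from about 50% to 70%.

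**The case against.** The strongest reply is that this is a defensible design. An independent service holds the list, research staff randomise only after consent and baseline, an audit trail is kept, and eligible refusers are monitored. Prioritisation of referrals is multi-agency, not one recruiter's choice. The same sentence that prints the sizes also specifies random blocks ("with a random block seeded throughout"). Their frequency is a detail that a randomisation service normally holds, and at 25% simple random they bring the bias near zero if severity is unknown.

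Much of this stands. A reader might infer several stronger things that the documents do not support:

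- **That staff will guess right 70% of the time, or that bias is 0.16 SD (60% of the target).** Both need the next severity stratum to be known before the GAIN-SS and no unbalanced blocks. The 0.2 SD shift has no source in the documents.
- **That the block of 2 is the culprit.** Dropping it alone takes the ceiling from 70.3% to 69.3%.
- **That printing the sizes is what gives the game away.** Picking the arm that is behind needs no sizes.
- **That the person who consents also keeps the running list.** The documents show the same organisation, not necessarily the same individuals.

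Small blocks also have a use in the pilot, where the balance criteria apply to only 60 people.

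What does not stand is the idea that the safeguards remove the problem. They hide the list but do not prevent inference from past allocations, and the documents set no separation between those who enrol and those who receive allocations. Guessing stayed above 50% in every scenario tried. Substance-use frequency is asked at first contact, so severity may be partly anticipated and the truth may lie between the two sets of figures.

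**Conclusion.** The concern holds as a cheap improvement, not as an error or contradiction. Allocations are partly predictable to the enrolling organisation: at most about 70% correct, about 64-65% with the next severity unknown, and about 60-63% if 10-25% of blocks are also simple random.

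On the assumed 75% action threshold and 0.2 SD shift, the bias runs from near 0 to 0.05 SD with severity unknown, and up to 0.16 SD at the ceiling. These figures show what is possible and are not forecasts. They rest on equally likely sizes, a 50/50 severity split, someone keeping the running record, and a random block whose form and frequency the protocol does not give. Where the bias is large enough to matter, 6/8/10 blocks cut it by at least half.

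**What to change.** From the start of the efficacy stage (340 of the 400 participants):

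1. Have the randomisation service use larger variable blocks without size 2 in each stratum, for example 6, 8 and 10, and keep the random blocks.
2. In the Randomisation section, replace the printed list of sizes with: *variable block sizes held by the randomisation service and not disclosed to Barnardo's or research staff*.

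Most of the gain comes from the larger blocks; withholding the sizes adds little but costs nothing. Leave the pilot list unchanged, because larger blocks would make the Appendix II balance criteria harder to meet with 60 participants.

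The cost is one configuration change and one sentence. The larger possible imbalance per stratum is negligible for precision at full size, and the primary model already adjusts for the strata.

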There is established evidence for MDFT in reducing substance use, delinquency and offending, improving adolescent mental health and prosocial behaviour, four systematic reviews (Baldwin et al., 2012, Filges T. et al., 2018, Tanner-Smith et al., 2013, van der Pol et al., 2017b) indicate it has a small to moderate effect size (δ = 0.20 to 0.30) when compared to other psychological therapies, with greater effects for those whose substance use is severe and those actively involved in offending. The established research base has limitations when

compared to the UK context, most studies have been conducted in the US, where business as usual tends to be more intensive than in the UK and studies conducted in Europe have tended to focus on cannabis use (Rigter et al., 2010). But MDFT has been successfully adapted to different contexts including comorbid substance use and mental health problems (Liddle et al., 2018), addiction to internet gaming (Nielsen et al., 2021), use among young adult populations (Liddle et al., 2024a), and different healthcare systems (Rigter et al., 2010).

MDFT has extensive evidence of being effective within diverse communities. For example, the 2008 evaluation by Liddle et al (Liddle et al., 2008) reports 71% of the population were African American and 11% Hispanic, whilst the population for the 2015 study by Dakof et al (Dakof et al., 2015) worked with a population which was 35% African American and 59% Hispanic.

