estimates found in systematic reviews of MDFT (Filges T. et al., 2018, van der Pol et al., 2017b). This equates to a number needed to treat of 6, where at least one in six participants receiving MDFT would show clinically important benefits, and a difference in the frequency of substance use of at least 13% in the MDFT group. Detecting an effect size smaller than this provides no additional benefit, the commissioning of services in England and Wales requires the service to achieve a clinically important difference for the target population. To detect this difference, with power at 80% and alpha of 0.05 and a two-tailed test, requires a sample of 480 participants followed-up at the 6-month endpoint. Using data from other studies of substance using adolescents (Coulton S et al., 2023, Deluca et al., 2020) we estimate the prepost-test correlation of the frequency of substance use to be 0.4, and incorporating this into the sample size calculation reduces the number followed-up to 364, 182 in each group. Assuming a loss to follow-up at the endpoint of 10%, similar to other studies in adolescent substance use populations (Coulton et al., 2024) inflates the number needed to randomise to 400. Assuming 80% of those eligible will be willing to consent an indication of acceptability of the study to participants and a lower figure than other studies in similar populations (Coulton et al., 2024) would mean we would need to approach 480 across both sites. Recruitment will be continuous between September 2025 and January 2027, 28 per month will need to be approached in total across both sites per month with the expectation that 24 will consent to participate in the trial across both sites. We anticipate. Based on relative population size that 40% of referrals will come from Newport and 60% from Bristol.

Table 2: Recruitment/ retention table

	Q1	Q2	Q3	Q4	Q5	Q6	Q7	Q8	Q9	Q10	Q11
Months (e.g. Oct-Dec 23):	May-Jul 25	Aug-Oct 25	Nov 25 - Jan 26	Feb - Apr 26	May-Jul 26	Aug-Oct 26	Nov 26 - Jan 27	Feb - Apr 27	May-Jul 27	Aug-Oct 27	Nov 27 - Jan 28
Target number of children and young people referred into the project	0	50	75	75	75	75	75	75	218	360	500
Target number of children and young people recruited to the project and evaluation	0	40	60	60	60	60	60	60	174	288	400
Target number of children and young people who withdraw/drop out	0	4	6	6	6	6	6	6	23	35	40

Table 3: Sample size calculations

		PARAMETER		
Minimum Detectable Effect Size (MDES)		0.27		

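### Two figures of 480 in the sample-size paragraph are wrong: the unadjusted number followed up should be 432 to 434, and the number to approach should be 500; the 364 analysed and the target of 400 stand

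*Protocol*

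**What the plan says.** The Protocol, Sample size calculations, builds the trial's size in a chain.

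- **Target effect:** "A clinically important effect size for substance use frequency in adolescents is estimated as 0.27, similar to the lower bound" of estimates in two cited systematic reviews. The section adds: "Detecting an effect size smaller than this provides no additional benefit".
- **Unadjusted size:** with 80% power and two-sided alpha 0.05, this "requires a sample of 480 participants followed-up at the 6-month endpoint".
- **Covariate adjustment:** a pre-post correlation of 0.4 brings the number followed up to 364, 182 per arm. Table 3 and the flow chart (Figure 3) repeat this.
- **Attrition:** 10% loss "inflates the number needed to randomise to 400".
- **Consent:** 80% of eligible young people are assumed to consent, which "would mean we would need to approach 480 across both sites". Recruitment is to be continuous from September 2025 to January 2027, with 28 approached and 24 consenting per month.

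Table 2, in the same section, ends at 500 referred and 400 recruited. In Study rationale and background, four systematic reviews, which include the two cited for the target effect, "indicate it has a small to moderate effect size (δ = 0.20 to 0.30").

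**The concern.** Each step should follow from the one before. Two do not. The unadjusted figure is larger than its inputs require and does not lead to the adjusted figure said to come from it. The approach figure does not deliver 400 at the stated consent rate and disagrees with Table 2.

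The stake is planning and traceability rather than validity. Under Pilot study analysis, the pilot is to confirm or revise this calculation, which is hard to do from a chain that cannot be reproduced. Appendix II sets 80% consent among eligible participants as a progression criterion. A pilot exactly at that level would look adequate, while the planned monthly approach rate would still leave recruitment short.

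**Working it through.** **Inputs**, all from Sample size calculations and Table 3: d = 0.27 in SD units, power 80%, two-sided alpha 0.05, equal allocation, r = 0.4, loss 10%, consent 80%, 17 months (September 2025 to January 2027 inclusive).

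**1. The adjusted figure, 364, reproduces.** Adjusting for a baseline covariate multiplies the variance by 1 − r² = 1 − 0.16 = 0.84. A two-sample t-test with effect 0.27/√0.84 needs 181.8 per arm, so 182 and 364 in total. The normal approximation gives 2 × (1.960 + 0.842)² × 0.84/0.27² = 180.9 per arm, so 181 and 362.

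**2. The unadjusted figure, 480, does not.**
- Normal approximation: 2 × (1.960 + 0.842)²/0.27² = 215.3 per arm, so 216 and 432 in total.
- t-test: 216.3 per arm, so 217 and 434 in total.
- Link to the next step: 480 × 0.84 = 403, not 364. Getting from 480 to 364 needs r = √(1 − 364/480) = 0.49. By contrast, 434 × 0.84 = 364.6.
- Possible origin: 432/0.90 = 480, so the figure may be the unadjusted number after 10% loss, mislabelled as followed up. This is an inference; the protocol does not say so.

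**3. The number to approach.**
- 400/0.80 = 500. The printed 480 equals 400 × 1.2; and 480 × 0.80 = 384 consenting.
- Table 2's quarterly entries from Aug–Oct 2025 to Feb–Apr 2027 sum to 50 + 6 × 75 = 500 referred and 40 + 6 × 60 = 400 recruited, which is 80%.
- Monthly: 24/28 = 86%, not 80%. At 80%, 28 × 17 × 0.80 = 381 consenting, 19 short of 400.
- Rate needed over the stated window: 500/17 = 29.4, so about 30; 30 × 17 × 0.80 = 408.

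**4. The recruitment window also varies.** The text gives 17 continuous months to January 2027. Table 2's quarters run to April 2027, at 25 referred and 20 recruited per month in most of them. The Timeline has 60 recruited in 09/25–12/25 and 340 in 07/26–05/27; over 11 months that is 340/11 = 31 randomised, or 39 approached, per month at 80%. The figure of 30 per month therefore holds only for the window in the sample-size text.

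**5. Attrition (minor).** 364/0.90 = 404.4, so 405. With 400 randomised and 10% loss, 360 remain, and power at 180 per arm is 79.6% against 80.0% at 182. The flow chart's 182 of 200 is 91% retention.

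**6. Position of 0.27 in the quoted range.** (0.27 − 0.20)/(0.30 − 0.20) = 0.7, so it lies toward the upper end. Power with 182 per arm and r = 0.4 (t-test):

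| Effect size | Power |
|---|---|
| 0.20 | 55% |
| 0.25 | 74% |
| 0.27 | 80% |
| 0.30 | 88% |

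**The case against.** The strongest reply is that nothing operative is wrong. The trial is sized on 364 followed up and 400 randomised. The first figure reproduces exactly, and the second is within about 1% of 405. The unadjusted 480 errs high and does not feed into either, and Table 2 already carries the correct 500. The pilot will re-examine the correlation, consent and retention. All of this stands, and it confines the point to correcting text.

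A reader might infer more in three places, and the documents do not support it.

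- **That the recruitment target is understated.** It is not. The target is 400 throughout; only the number to approach is short, by 20.
- **That 55% power at 0.20 shows the trial is too small.** The protocol presents 0.27 as the clinically important difference and declines to power below it, which is a legitimate choice. The 55% is a sensitivity figure. The two passages on effect size are also not fully like for like: one cites two reviews, the other summarises four, with "0.20 to 0.30) when compared to other psychological therapies" as the comparison, whereas this trial compares with business as usual. The reviews cannot be checked here. What remains is that the lower-bound wording does not sit with the protocol's own range.
- **That the number needed to treat and the 13% difference are errors.** The text says "This equates to a number needed to treat of 6" and adds a difference of at least 13% in frequency of use. These are different quantities. Showing either to be wrong needs an SD, a control response rate or an absolute reading of the 13%, none of which the protocol gives.

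**Conclusion.** The point holds for two printed figures and the monthly rate derived from the second. The unadjusted number followed up is about 10% too high (480 against 432 to 434) and is inconsistent with the 364 said to follow from it. The number to approach is 20 too low (480 against 500), contradicts Table 2, and at 80% consent would leave about 381 recruited over the stated 17 months. These results use only the protocol's inputs and standard two-sample formulas; other combinations of alpha, power and sidedness, and a change-score analysis, do not yield 480 followed up either.

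The sample of 364 analysed is right for d = 0.27 and r = 0.4. Randomising 400 rather than 405 costs about 0.4 percentage points of power. The lower-bound wording is an inconsistency of justification, not of arithmetic.

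**What to change.** In Sample size calculations:

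1. Replace 480 followed up with 434. If 480 was meant as the unadjusted number after 10% loss, label it as randomised instead.
2. Change the number to approach to 500 and the monthly rate to about 30 for the stated window. Then settle on one recruitment window across the text, Table 2 and the Timeline, and recompute the rate if the window changes.
3. State either 9% loss with 400 randomised (400 × 0.91 = 364) or 10% loss with 405.
4. Reword the lower-bound description so that it agrees with the range of 0.20 to 0.30 in the background, or state which estimates in the two cited reviews it refers to. Power at 0.20 and 0.25 may be added as sensitivity figures.

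The cost is a text amendment. If 9% loss is stated under item 3, the 400 randomised is unchanged, and the 364 analysed and the analysis do not change in either case. The practical cost is approaching 20 more young people than the paragraph now says, which Table 2 already plans for.
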